## 1. Background Information

### 1.1 Introduction

Urinary incontinence is a complaint of involuntary leak of urine. When it becomes serious, urinary incontinence markedly lowers quality of life (QOL) by discouraging patients from going out or making them always concerned about urination. There are various types of urinary incontinence, which can be roughly divided into urgency urinary incontinence (UUI), stress urinary incontinence (SUI) and mixed urinary incontinence (MUI). UUI is a complaint of involuntary leak of urine at the same time or immediately after urgency. SUI is a complaint of involuntary leak of urine at the time of exertion or exercise, or during sneezing or coughing. MUI is a symptom in which UUI and SUI are observed. It is a complaint of involuntary leak of urine associated not only with urgency, but also with exercise, exertion, sneezing and cough.

No full-scale epidemiological survey of urinary incontinence has been conducted in Japan and therefore, exact prevalence is unknown. On urinary incontinence in women, some studies of its prevalence have been conducted and the results have been reported since around 1986. The prevalence of urinary incontinence in otherwise healthy women without disorders other than urinary incontinence has been reported to be 10% to 46%. SUI is more prevalent than UUI and the frequency of UUI increases with age. In Japan, MUI is observed in approximately 20% of women. Moreover, in an epidemiological study of people aged 40 years or older by the Japanese Continence Society, SUI occurred once a week or more frequently in 12.6% and 3.0% of women and men, respectively, confirming that SUI is more common in women. When women were analyzed by generation, SUI peaked in their forties and fifties and decreased after that. In contrast, the prevalence of MUI rose sharply at the age of no less than 60 years, at which SUI started to decrease. These results suggest that symptoms of SUI are universal among people aged 40 years or older. In addition, along with nocturia, SUI is considered to lower the QOL most greatly among urination disorders in women. This tendency is prominent in women in their forties to sixties. Therefore, women in these generations who are actively involved in the society are speculated to be bothered especially by SUI. As the society ages and women make more advances in society, treatment of SUI is considered to have a greater social significance.

The factor for onset of SUI is decrease in urethral resistance and resulting increase in intravesical pressure in response to abdominal pressure to the level exceeding urethral resistance. Thus, urine leaks without bladder contraction. The main pathological conditions that cause decrease in urethral resistance are urethral hypermobility and intrinsic sphincter deficiency (ISD). In urethral hypermobility, pelvic floor muscles that support pelvic viscera relax, the bladder neck droops down and the support by pubourethral ligament becomes insufficient. Therefore, urethra tends to dilate when there is abdominal pressure, resulting in urinary leak. In ISD, urinary sphincter itself becomes weak, bladder neck and proximal urethra dilate even at rest and mild increase in bladder pressure in response to abdominal pressure causes urinary incontinence. ISD may be caused by atrophy of urethral mucosa due to postmenopausal decrease in estrogen or changes in urethra due to surgical treatment of urinary incontinence or gynecological surgery. However, the causes are unknown in many cases. ISD is also considered to be caused by disorders of external urethral sphincter that are iatrogenic or based on traumas or neurological diseases. The smooth muscles in bladder

neck or proximal urethra that correspond to internal urethral sphincter contract when the sympathetic nerve (hypogastric nerve) is stimulated being mediated by  $\alpha_1$  receptor. Prostatic smooth muscles in men have a similar contraction mechanism mediated by  $\alpha_1$  receptor. The external urethral sphincter and pelvic floor muscles are predominantly innervated by somatic nerve (pudendal nerve) and their contraction is mediated by nicotinic acetylcholine receptor.

UII is mainly treated by drug therapy. Anticholinergics or  $\beta_3$  adrenergic receptor agonists are used. Therapeutic methods for SUI include physical therapy (pelvic floor muscle training), drug therapy ( $\beta_2$  adrenergic receptor agonists) and surgical therapy (urethral sling surgery). Pelvic floor muscle training is expected to be effective when implemented for a long term. However, not so many patients continue it for a long term. Urethral sling surgery is widely performed for SUI in women and favorable results have been obtained. Nevertheless, its disadvantage is that it requires placement of a foreign object inside the body. Vaginal erosion and other conditions caused by the material of the foreign object, the sling, have been reported as complications. In drug therapy, a  $\beta_2$  adrenergic receptor agonist, clenbuterol, is the only drug covered by insurance in Japan. Clenbuterol is rated as the recommendation grade B in Clinical Guideline for Female Lower Urinary Tract Symptoms. As it increases the contractility of external urethral sphincter and relaxes the detrusor muscle, it is expected to improve the symptoms of SUI. However, it needs to be administered carefully in patients with hypertension or heart disease. Thus, development of noninvasive and effective drugs for SUI is desired.

[REDACTED]

[REDACTED]

## **1.2 TAS-303 [investigational drug]**

The investigational drug is a white tablet containing 1 mg of TAS-303.

### **1.2.1 Mechanism of Action**

[REDACTED]

## **1.3 Placebo [Comparator]**

The placebo, which is the comparator, is a tablet that does not contain the active ingredient of the investigational drug and is indistinguishable from the investigational drug in appearance.

## **1.4 Known and Potential Benefits and Risks**

### **1.4.1 TAS-303**

#### **1.4.1.1 Potential Benefits**

In drug therapy for SUI, a  $\beta_2$  adrenergic receptor agonist, clenbuterol, is the only drug covered by insurance in Japan. Clenbuterol is rated as the recommendation grade B in Clinical Guideline for Female Lower Urinary Tract Symptoms. As it increases the contractility of external urethral sphincter and relaxes the detrusor muscle, it is expected to improve the symptoms of SUI. However, it needs to be administered carefully in patients with hypertension or heart disease. Thus, development of noninvasive and effective drugs for SUI is desired.

[REDACTED]

Among clinical studies conducted so far, subjects of Study 10060010, Study 10060020

and Study 10060030 were healthy adults and therefore, benefits to subjects were not evaluated. Ongoing Study 10060040 is a Phase I study in patients with SUI and its objectives are pharmacodynamic and pharmacokinetic examination and evaluation of tolerability of TAS-303. The improvement of SUI symptoms by TAS-303 is not evaluated.

#### 1.4.1.2 Possible Safety Risks

the first time in the history of the world, the people of the United States have been called upon to decide whether they will submit to the law of force, and let a一小部分 of their country be destroyed, or whether they will, in the spirit of the Declaration of Independence, assert their right to self-government, and save their country.

[REDACTED]

[REDACTED]

#### 1.4.2 Drugs with Similar Mechanism of Action to That of TAS-303

As drugs with the same mechanism of action as that of TAS-303, which is an inhibitory action on NA reuptake, atomoxetine hydrochloride and amezinium metilsulfate are on the market. The main adverse reactions to atomoxetine hydrochloride are shown in [Table 1.4.2-1](#) and the main adverse reactions to amezinium metilsulfate in [Table 1.4.2-2](#). As serious adverse reactions to atomoxetine hydrochloride, hepatic function disorder, jaundice, hepatic failure (incidence unknown) and anaphylaxis (incidence unknown) have been reported.

Table 1.4.2-1 Main Adverse Reactions to Atomoxetine Hydrochloride

Category of adverse reactions	5% or higher	1% or higher and less than 5 %
Gastrointestinal	Nausea, decreased appetite, abdominal pain, vomiting, constipation, thirst	Diarrhoea, dyspepsia, dry mouth
Neuropsychiatric	Headache, somnolence, dizziness	Dizziness postural, sleep disorder, irritability, dysphoria, insomnia
Hypersensitivity	-	Pruritus
Cardiovascular	Palpitations	Tachycardia, blood pressure increased, heart rate increased
Dermatological	-	Hyperhidrosis
Urogenital	-	Dysuria, erectile dysfunction
Other	Weight decreased	Chest pain, asthenia, fatigue, hot flush, chills, dysgeusia

Table 1.4.2-2 Main Adverse Reactions to Amezinium Metilsulfate

Category of adverse reactions	0.1% or higher and less than 5 %
Gastrointestinal	Queasy/vomiting, abdominal pain
Neuropsychiatric	Giddiness, dizziness on standing up, headache, heaviness of head, feels poorly
Cardiovascular	Palpitations, tachycardia, blood pressure fluctuation, arrhythmia (eg., extrasystoles, atrial fibrillation), feeling of hot flushes, feeling of hot flash
Hepatic	Hepatic function abnormal including AST increased and ALT increased
Other	Urination impaired

#### **1.4.3 Estimated Benefits and Risks for This Study**

In the evaluation of the number of urinary incontinence, the amount of urinary incontinence, QOL and other parameters in this study, improvement of urinary incontinence by TAS-303 can be expected in participating patients. Additionally, safety and dose response in 8-week administration of TAS-303 at a dose of 3 mg or 6 mg can be discussed and the recommended dose can be estimated.

### **1.5 Key Findings and Experiences**

#### **1.5.1 Nonclinical Findings**

Refer to the Investigator's Brochure.

#### **1.5.2 Clinical Experiences**

##### **1.5.2.1 Phase I single-dose study (Study 10060010)**

[REDACTED]

###### **1.5.2.1.1 Pharmacokinetics**

[REDACTED]

###### **1.5.2.1.2 Safety**

[REDACTED]

[REDACTED]

[REDACTED]

[REDACTED]

#### **1.5.2.2 Phase I multiple-dose study (Study 10060020)**

[REDACTED]

##### **1.5.2.2.1 Pharmacokinetics**

[REDACTED]

[REDACTED]

[REDACTED]

[REDACTED]

[REDACTED]

### 1.5.2.2.2 Safety

### 1.5.2.3 Drug Interaction Study with Simvastatin/Midazolam (Study 10060030)

1.5.2.3.1 Pharmacokinetics

1.5.2.3.2 Safety

#### 1.5.2.4 Phase I Study in Patients with SUI (Study 10060040)

[figure not shown]
The study period was completed and the clinical study report is currently being prepared.

### 1.6 Rationale for Study and Selection

#### 1.6.1 Study Population

The subjects of this study are female patients with SUI aged 20 years or older and younger than 80 years who present with a stable pathological condition, have subjective symptoms of SUI and were diagnosed with SUI objectively. To make the study population uniform as much as possible, the administration of placebo during the observation period using single-blind design and the exclusion of patients who responded considerably to placebo as ineligible at the time of enrollment in the treatment period were planned.

#### 1.6.2 Study Design

[REDACTED]

[REDACTED]

[REDACTED]

### **1.6.3 Selection of TAS-303 Doses**

As the doses of TAS-303 in this study, 3 mg and 6 mg were selected.

[REDACTED]

[REDACTED]

[REDACTED]

[REDACTED]

[REDACTED]

### **1.6.4 Selection of Placebo**

Based on the high placebo effect in the treatment of SUI as is the case with the treatment of overactive bladder (OAB) and referring to the design of studies on duloxetine, an observation period for the administration of placebo using single-blind design was planned to exclude, as much as possible, the patients who respond considerably to placebo.

In order to objectively evaluate the efficacy and safety of TAS-303, the placebo group was formed for the treatment period. Use of placebo group is recommended in Guideline on the Clinical Investigation of Medicinal Products for the Treatment of Urinary Incontinence of EMA and FDA guidelines.

## **2. Objectives and Endpoints**

### **2.1 Primary Objective**

To examine the efficacy of TAS-303 using the rate of change in the number of urinary incontinence as an index and placebo as control, in female patients with SUI

### **2.2 Secondary Objectives**

- (1) To examine the efficacy of TAS-303 using the changes in the variables including ICIQ-SF score or I-QOL score as indices and placebo as control, in female patients with SUI
- (2) To examine the dose response of TAS-303 in improvement of urinary incontinence in female patients with SUI in an exploratory manner
- (3) To examine the safety of TAS-303 using the status of onset of adverse events and other indices in female patients with SUI

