### **13.1.3 Statistical Analysis Methods**

The main statistical methods to evaluate the primary and secondary objectives of this study are described below.

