2.2.2. Rationale for Sample Size Determination

The number of patients was determined, assuming that efficacy comparable to that of duloxetine can be expected based on results of nonclinical studies. Based on the mean rate of change in the number of urinary incontinence of -62.28% in the duloxetine group and -41.86% in the placebo group from data of a clinical trial of duloxetine, Yentreve clinical study results, Trial ID #6231, the difference between the TAS-303 6-mg or 3 mg group and the placebo group in the rate of change in the number of urinary incontinence, which is the primary endpoint of the present study, was assumed to be -20%. From the standard deviation of 33.73% in the duloxetine group and 32.08% in the placebo group in the above study data, the standard deviation common in two groups was assumed to be 35%. Using the two-sided significance level of the entire test of 5% and the two-sided significance level of each test of 2.5% by Bonferroni's method, when the statistical power is specified as 90% and the rate of withdrawal in the treatment period as about 5%, the number of patients necessary for confirmation of a significant difference between the TAS-303 group and the placebo group is approximately 250 (83 per group).

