3.2. Analysis Populations

The name of analysis populations and their definitions are shown in Table 3-2. The handling of patients with problems in terms of their attribution apart from the criteria shown below will be determined through discussion by the sponsor, the medical experts, and other personnel. The primary efficacy analysis population is PPS while the primary safety analysis population is all treated population.

Table 3-2 Definition of Analysis Populations

Analysis Populations	Definition
All screened population	All patients who gave informed consent
All observation period enrolled population	All patients enrolled in the observation period of this study
All treatment period enrolled population	All patients enrolled in the treatment period of this study
All treated population	Patients in the all observation period enrolled population who have received at least 1 dose of the study drug.
Full Analysis Set(FAS)	Patients in the all treatment period enrolled population who have received at least 1 dose of the study drug for the treatment period and have at least 1 available efficacy endpoint before start of the treatment period and during the treatment period.
	Patients in FAS who have not met any of the following criteria: (1) Patients that have violated any inclusion criteria (2) Patients that have met any exclusion criteria (any criteria that affects the efficacy evaluation)
Per Protocol Set(PPS)	(3) Patients whose compliance rate is < 80% during the treatment period (4) Patients whose rate of completion of Bladder diary (status of urinary incontinence) is < 70% at Week 8 of treatment
	(5) Patients that have received any prohibited concomitant medications or prohibited concomitant therapies that may affect the efficacy evaluation

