6.2.2. Statistical Methods

6.2.2.1. Summary Statistics of Continuous Volume

When summary statistics of continuous volume is provided, it should also show the sample size, minimum, maximum, first quartile, median, third quartile, mean, and standard deviation.

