7.3. Secondary Analyses of Primary Endpoint

Following analyses will be performed in FAS and PPS:

- Summary statistics will be calculated for each treatment group. Missing values will not be imputed.
- For percent change in the mean IEF per 24 hours from baseline at each week, mixed-effect models for repeated measures (MMRM) will be performed using treatment groups, evaluation time points (Week 4 and Week 8 of treatment), and interactions between the treatment group and the evaluation time point as fixed effects, and allocation factors (status of urinary incontinence [SUI or MUI], mean IEF per 24 hours [≥ 2 per day or < 2 per day]) and age (≥ 60 years or < 60 years) as covariates. Thus, the least mean square (LS Mean) in each treatment group and the difference in the LS mean between each dose group and the placebo group and the two-sided 95% CI will be estimated at Week 8 of treatment. Unstructured covariance structure will be assumed, and toeplitz type will be used in case of no convergence. If convergence is still not achieved, the First-order autoregressive → Compound symmetry → Variance component will be used in this order. The Kenward-Roger method (2009)⁴⁾ will be used to calculate degrees of freedom.
- Intergroup comparison will be conducted using the placebo group as the control by the van Elteren test⁵⁾ using Wilcoxon rank sum test and allocation adjustment factors and age (< 60 years and ≥ 60 years) as strata. If any stratum includes a group with 0 patient, the test will be conducted by excluding age from the strata. The van Elteren

test will be performed in two patterns, i.e., a pattern in which allocation adjustment factors at the time of enrollment are used as strata (analysis in the FAS only) and a pattern in which allocation adjustment factors recorded in CRF are used as strata. Missing data will be imputed using LOCF.

• The time profile of percent change from the baseline will be graphically presented by treatment group.

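### Does the exploratory dose-response objective need its own 6 mg minus 3 mg contrast in the SAP?

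*Protocol*

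**What the plan says.** Protocol 2.2 gives as its second secondary objective "To examine the dose response of TAS-303 in improvement of urinary incontinence in female patients with SUI in an exploratory manner". Protocol 1.4.3 adds that safety and dose response at 3 mg and 6 mg "can be discussed and the recommended dose can be estimated". Protocol 13.1.3 opens by saying "The main statistical methods to evaluate the primary and secondary objectives of this study are described below".

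The planned efficacy comparisons all use placebo as control:

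- The primary analysis (SAP 7.1) tests 6 mg against placebo and 3 mg against placebo in the PPS, with Hochberg's adjustment.
- The Week 8 MMRM (SAP 7.3) estimates a mean for each treatment group and "the difference in the LS mean between each dose group and the placebo group", with a two-sided 95% interval, in both FAS and PPS.
- SAP 8.1.11, 8.1.12 and 8.1.14 add analyses in which the two doses are pooled.

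Several outputs are given by dose group. SAP 7.3 states "Summary statistics will be calculated for each treatment group. Missing values will not be imputed", and SAP 6.2.2.1 says of such summaries that "it should also show the sample size, minimum, maximum, first quartile, median, third quartile, mean, and standard deviation". SAP 7.3 also plans a graph of percent change over time by group. SAP 8.1.1 plans the proportion with at least a 50% reduction in each group, with its interval. SAP 12 says that only major analyses are listed in the SAP and that the full list is in the Table and Figure Plan.

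**The concern.** The protocol promises methods for the secondary objectives. The efficacy-score objective and the safety objective each have clearly matching analyses, but dose response has none: no trend test, no dose-response model and no direct comparison of the doses. Pooling the two doses removes the information that this objective needs.

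The design does not fill the gap. SAP 2.2.2 assumes one value, a 20-point reduction, for "the difference between the TAS-303 6-mg or 3 mg group and the placebo group", so the step from 3 mg to 6 mg was never a sizing target. If a recommended dose is to be discussed, the uncertainty of that step matters. Without a printed interval, a reader might take two similar estimates as equal doses, or take one significant and one non-significant placebo comparison as proof that the doses differ. A reader who combined the two placebo intervals as if they were independent would get the wrong width. One contrast from the planned MMRM would seem to settle this at almost no cost.

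**Working it through.** **Inputs.** From SAP 2.2.2: difference from placebo 20 points for either dose, common SD 35, two-sided 2.5% per comparison, power 90%, withdrawal about 5%, 83 per group. From Protocol 3: allocation 1:1:1.

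**1. The plan's own figure.** Normal formula: n = 2 × (2.241 + 1.282)² × (35/20)² = 76.02, so 77 per group; 77/0.95 gives 82. The exact t calculation gives 78 per group; 78/0.95 gives 83, or 249 in all. The stated 83 per group and approximately 250 reproduce.

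**2. Precision of 6 mg minus 3 mg.** Evaluable patients per arm: 83 × 0.95 = 78.85, taken as 79.

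- SE = 35 × √(2/79) = 5.57
- Half-width = t(0.975, 156) × 5.57 = 11.0 points

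The half-width is 10.1 at SD 32.08 (the placebo SD in the duloxetine data), 12.6 at an assumed SD of 40, and 11.7 with an assumed 70 per arm. It is 10.4 or 9.2 if covariates explain an assumed 10% or 30% of the variance.

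**3. Does the contrast say anything the placebo contrasts do not?** With n per arm and common variance σ²:

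- Variance of each placebo contrast: 2σ²/n = 2 × 1225/79 = 31.01
- Covariance from the shared placebo arm: σ²/n = 15.51
- Variance of 6 mg minus 3 mg: 31.01 + 31.01 − 2 × 15.51 = 31.0, so SE 5.57

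The result is the same as for each placebo contrast. The point estimate is the 6 mg minus placebo difference less the 3 mg minus placebo difference. Ignoring the covariance gives √62.02 = 7.88 and a half-width of 15.6, which is 1.41 times too wide.

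**4. Does this survive covariates and unequal arms?** A simulated three-arm linear model with three binary covariates, a single-visit stand-in for the MMRM (SD 35, 79 per arm), gave a mean half-width of 11.01 for 3 mg minus placebo, for 6 mg minus placebo and for 6 mg minus 3 mg. With assumed arms of 80 (placebo), 65 (3 mg) and 75 (6 mg), the direct contrast had half-width 11.72. Recovering it from the two placebo intervals and the arm sizes also gave 11.72, with a mean error of 0.4% (95th percentile 1.3%). The arm sizes are among the planned summary statistics.

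**5. A linear summary.** For equal arms at 0, 3 and 6 mg, the least-squares slope is (mean at 6 mg − mean on placebo)/6. The 3 mg arm sits at the centre and drops out. A planned contrast divided by 6 therefore gives the slope.

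**6. What the contrast could show.** At a two-sided 5% level with 79 per arm, power for an assumed true dose difference of 5, 10 or 15 points is 14%, 43% or 77%. It can serve as an estimate but not as a test on which to choose between the doses.

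**The case for a change.** The strongest case for a change is that Protocol 13.1.3 claims to cover the secondary objectives and visibly passes over this one. The remedy is one contrast in a model already being fitted. It needs no new data and spends no alpha, because SAP 11.5 confines the Hochberg adjustment to the primary objective. A printed interval of about ±11 points, against an assumed drug effect of 20, would warn readers that the doses may not be separable.

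Part of this stands. No output carries the objective's label, the direct contrast is not listed, and printing it would be harmless and convenient. It is slightly more than one row per population. The PPS, of which SAP 3.2 says "The primary efficacy analysis population is PPS while the primary safety analysis population is all treated population", needs one model, but SAP 6.2.3 runs FAS analyses that use the allocation factors in two patterns, with CRF values and with IWRS values.

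The rest does not carry. The objective asks for an exploratory examination, and nothing in the documents equates dose response with the 6 mg minus 3 mg step. The sentence in Protocol 1.4.3 belongs to the benefit and risk text and commits to no method. The interval that is too wide by 41% arises only if a reader treats contrasts with a common control as independent; no rule in the plan leads there. Reading similar estimates as equivalence is likewise a matter for how results are discussed.

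**Conclusion.** No change is needed. The visible plan does not leave the objective without an analysis: the per-dose means, placebo differences with intervals, responder proportions and time plot are a sensible exploratory description of two doses and placebo. What is missing is a label and one derived line. That line's estimate follows by subtraction. Its half-width, about 11.0 points unadjusted (9.2 to 12.6 over the assumptions tried), is essentially that of each planned placebo contrast.

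This rests on near-balanced arms and a variance common to the groups; moderate imbalance did not disturb it. The adjusted result was checked in a single-visit model and not in the MMRM itself. An unlisted contrast also cannot be ruled out, because the Table and Figure Plan was not available and the design and dose rationales are redacted. The primary test, multiplicity control and sample size are unaffected either way.
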